3.6.5 Early discontinuation visit

If a patient discontinues after randomization but prior to completion of the study treatment period, the patient will be asked to return as soon as possible to the study site for an early discontinuation (ED) visit. The patients will not receive exenatide or placebo; however, a treatment regimen, as deemed clinically appropriate, should be initiated. Investigative staff

should complete a study summary page for each patient. Patients who discontinue early from the study treatment period should continue into the safety follow-up addendum unless the patient is lost to follow-up, withdraws consent, or achieved final height criteria of a change of less than 5 mm during the treatment period.

3.6.6 Study periods

The following definitions will be used to assign data to the correct study period. For details on which data will be presented in outputs for each endpoint, refer to Section 4.2.

Pre-treatment period: defined as the period prior to the date of the first dose of randomized study medication. All data for patients who do not receive randomized study medication will be considered pre-treatment.

Treatment period: defined as the date of first dose of randomized study medication to date of the Week 28 visit, or the ED visit for patients who discontinue the study prior to Week 28.

Safety follow-up period: defined as the day after the Visit 11 (Week 28) visit, or the day after the ED visit for patients who discontinue the study prior to Visit 11 to the date of completion of the Safety follow-up study (typically after 3 years or once the patient has a height difference of less than 5 mm between two 6-month interval visits). The safety follow-up period will only be defined for patients who enter the safety follow-up period.

See Section 4.1.3 for details on missing data handling.

4 ANALYSIS METHODS

4.1 General principles

All statistical evaluations, as well as summaries and tabulations, will be done by qualified personnel at IQVIA. Before unblinding, following clean file declaration (database lock), all decisions on the evaluability of the data for each individual patient will be made and documented and each patient will be assigned to the appropriate analysis set.

Statistical analysis software (SAS) version 9.4 or later will be used to generate all statistical analyses, data summaries and listing.

4.1.1 Statistical notations and presentations

Although patients randomly assigned to placebo will be assigned to take the volume equivalent to 5 µg exenatide twice daily or to take the volume equivalent to 10 µg exenatide twice daily, all patients assigned to placebo will be combined into 1 group for analysis purposes. Descriptive summaries will present treatment groups separately, as follows:

5 µg EBID	10 µg EBID	Total EBID	Placebo	Total
EBID Exenatide twice daily				

Total EBID is the pool of the 10 µg and 5 µg EBID doses. Total (over all treatments) will not be included in efficacy and safety endpoint outputs.

Summaries including data from the safety follow-up period will be presented by the actual treatment group during the randomized period.

All efficacy and safety variables will be summarized using descriptive statistics as appropriate. Continuous variables will be summarized by descriptive statistics including n (number of patients with available data), arithmetic mean, standard deviation (SD), median, minimum value and maximum value. The mean and median will be presented with one more decimal place than the original data; the standard deviation with two more decimal places than the original data; and minimum and maximum values with the same number of decimal places as the original data. Categorical variables will be summarized using frequency tables (number of patients and percentage of patients in each category). Unless otherwise stated, percentages will be calculated out of the analysis set total for the treatment group. Percentages will be rounded to one decimal place.

For log transformed data, the following descriptive statistics will be presented: n (number of patients with available data), geometric mean, geometric coefficient of variation (GCV%), geometric standard deviation factor (GSD), arithmetic mean, standard deviation, coefficient of variation (CV%), median, minimum and maximum value.

GCV (%) will be calculated as

$$100 \cdot \sqrt{(\exp(s^2) - 1)}$$

where s is the SD of the data on a log scale.

Individual data will be presented in patient listings. All patient data listings will be sorted by treatment and patient identifier ID. The first 3 digits of the patient ID denotes the center number and the next 4 digits denotes the individual patient number.

4.1.2 Hypothesis testing significance level

Statistical tests, where performed, will be conducted at a 2-sided significance level of 5%. Where appropriate, model-based point estimates, together with their 95% confidence intervals will be presented along with the 2-sided p-values for the tests.

No adjustments for multiplicity (including hierarchical testing) will be made for the primary, secondary and exploratory variables.

4.1.3 Handling of missing data

4.1.3.1 Missing efficacy data

Missing data in this study may result from patients discontinuing from the study prematurely or missing intermediate visits or selected assessments while remaining on study. Every effort will be made to obtain the CSP-required data for all study assessments that are scheduled for all patients who have been enrolled. Data collected after initiation of rescue therapy will be excluded from most efficacy analyses (see Section 4.2.4 for details) and therefore these data will effectively be handled as missing in analyses. For efficacy analyses, in general missing observations will not be imputed, except those inherited from the mixed model repeated measures (MMRM) which implicitly assumes that data are missing at random (MAR).

Sensitivity of the primary analysis will be performed using pattern mixture model imputation for missing values and details of this imputation is provided in Section 4.2.4.3.

Missing at Random (MAR) refers to missingness that is independent of missing responses, conditionally on observed responses and covariates. As the imputation strategy should always consider the dropout patterns and the time-course of the efficacy measurements by treatment, the pre- and post- withdrawal values will be assessed to understand the impact of dropouts on the efficacy results. The primary efficacy endpoint of HbA1c data will be visually examined to explore the missingness patterns by (1) plotting each individual patient's HbA1c change trajectory in completers, side-by-side with those from the early study drug withdrawal, and by (2) plotting the early study drug withdrawal's last HbA1c change data, overlaid with the box plot by visit from completer population.

For categorical endpoints HbA1c goals of <6.5%, ≤6.5% and <7% at 28 weeks, any patient with missing HbA1c value at 28 weeks will be considered as failed to meet HbA1c <6%, ≤6.5% and <7%, respectively, at endpoint (28 Weeks).

4.1.3.2 Missing baseline and demographic data

For demographic and baseline characteristics, each variable will be analyzed and/or summarized using the available data. For continuous variables, missing data will be indicated in the “n” count and for categorical variables, patients with missing data will be included in the “Total” count and denominator for percentages.

4.1.3.3 Missing safety data

Safety analyses will be conducted on the observed case (OC) only.

However, imputation of missing or partial AE and concomitant medication onset/start, and end/stop dates will be used to determine the status of each AE and the previous/concomitant status of each medication. See [Appendices 3 and 4](#) for the method of imputation of missing/partial AE/concomitant onset/start and end/stop dates. Missing/partial start/stop dates will appear as is (i.e., without imputation) in the patient data listings, but will be imputed to permit the proper tabulation of AE and concomitant medications data.

In addition, in case of missing AE severity, AE causality, or AE seriousness, a worst-case approach will be used. For missing severity, the AE will be considered severe; for missing causality, the AE will be considered as possibly-related to study drug; for missing seriousness, the AE will be considered serious.

4.1.3.4 Premature discontinuation

Patients who discontinue study medication prior to Visit 11 (Week 28) should enter the safety follow-up period, unless they have a height difference of less than 5 mm over a 6-month interval at study-site visits prior to discontinuation of study medication.

Patients who discontinue the study prematurely should have all early termination visit procedures done at the time of study discontinuation.

4.1.4 Handling of data post rescue medication

Instances of patients receiving rescue medication is defined in Section 3.6.4.

Efficacy

For all efficacy endpoints data collected after the first administration of rescue therapy will be excluded from the descriptive statistical summary and inferential statistical analyses.

However, data collected after initiation of rescue medication will be included in several sensitivity and supportive analyses for the primary analysis to provide a comprehensive view of the treatment effect (see more details in Section 4.2.4.3).

Safety

Because patients can continuously receive study medication concurrent with the rescue therapy, all safety data (except eGFR) collected during the rescue medication use will be summarized together with data collected prior to the rescue therapy. The exploratory analysis of eGFR will be repeated twice (once including data after rescue therapy and once excluding data after rescue therapy).

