3.6.4 Rescue therapy

Rescue therapy is defined as any new antidiabetic concomitant medication or changes to background oral-diabetic medication, for exacerbation of diabetes.

Treatment with insulin may be given for emergency reasons during the treatment period. If the period of insulin use exceeds 10 days during a 3-month period, then a decision to discontinue study treatment will be made after consultation between the investigator and the Sponsor's clinical research physician.

Background oral antidiabetic medication (metformin and SU) were to be continued throughout the study at the same dose and schedule as before study entry. However, metformin dosage could be adjusted for up to 10 consecutive days or 10 days in a 30-day period and the SU dosage could be decreased in response to hypoglycemia.

Changes in background metformin and SU will be programmatically derived from the concomitant therapy (CCT) oral anti-diabetic medication (OAM) CRFs and reviewed by the clinical team prior to unblinding. Increases identified as potential rescue episodes will be queried at the site-level to determine whether rescue therapy or not.

New antidiabetic medication will be programmatically identified from the CCT OAM CRFs where the Anatomical Therapeutic Chemical (ATC) code begins with "A10".

A rescue episode will be defined as the first unique rescue therapy entry on the CCT OAM CRFs as derived as above. If a patient has multiple entries, the first will be considered the point at which the patient was rescued.

For patients who require initiation of rescue therapy and continue study treatment, only data before initiation of rescue therapy will be included in the primary efficacy analysis. If HbA1c is measured before rescue therapy, then we will include the HbA1c measurement. If HbA1c is measured on the date of first rescue therapy but no time information is available, then HbA1c will be included in the primary efficacy analysis. Sensitivity analyses including data after initiation of rescue therapy will be carried out to test the robustness of the missing data assumption.

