4.2.5.2 Hypoglycemic episodes

Confirmed hypoglycemic episodes will be defined as follows:

Minor hypoglycemia:

- Any time a patient feels that he or she is experiencing a sign or symptom associated with hypoglycemia that is either self-treated by the patient or resolves on its own and
- Has a concurrent fingerstick blood glucose <3.0 mmol/L (54 mg/dL).

Major hypoglycemia:

- any episode with symptoms consistent with hypoglycemia resulting in loss of consciousness or seizure that shows prompt recovery in response to administration of glucagon or glucose or
- documented hypoglycemia (blood glucose <3.0 mmol/L [54 mg/dL]) requiring the assistance of another person because of severe impairment in consciousness or behavior (regardless of whether symptoms of hypoglycemia are detected by the patient).

Episodes will be categorized into major or minor following medical review of the hypoglycemic data by an AstraZeneca or IQVIA physician.

Incidence of hypoglycemic episodes will be summarized by whether they are major or minor and by when the episodes occurred (night-time will be defined to be between 11pm and 5 am) using frequencies and percentages of patients with at least one episode of hypoglycemia occurring during the study. The number of episodes per patient will be classified into categories (0, 1 to 2, 3 to 4, ≥ 5), and summarized using frequencies by treatment group and visit for the Safety analysis set.

Similar analyses will be performed for confirmed hypoglycemic episodes (those with a blood glucose record) and unconfirmed hypoglycemic episodes (those reported into study database without corroborating blood glucose record).

Minor and Major hypoglycemia rate (adjusted for duration of exposure to study drug therapy = the date of last dose of IP – date of first dose of IP +1) will be summarized by treatment.

The number and percentage of patients with any confirmed and unconfirmed hypoglycemic episodes will also be summarized by baseline sulfonylurea use (yes/no) and treatment.

Hypoglycemic events will be listed.

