An ANCOVA analysis of change in eGFR from baseline to Week 28 by baseline eGFR (hyperfiltrating: ≥ 125 ml/min/1.73m² versus non-hyperfiltrating: < 125 ml/min/1.73m²) will be provided. The same multiple imputation approach as stated in Section 4.2.4.4 will be used. The model will include treatment, screening HbA1c strata ($\leq 8\%$, $> 8\%$), background diabetes therapy strata (drug naïve, metformin only, SU only, and metformin + SU), baseline eGFR as the fixed effects. The least squares mean, 2-sided 95% confidence interval, and p-value of the difference in the endpoints of interests between Total EBID and PBO groups will be presented. This analysis will be done both excluding data after initiation of rescue therapy and separately including data after initiation of rescue therapy.

eGFR will also be calculated using the Chronic Kidney Disease Epidemiology Collaboration (CKD-EPI) formula (Levey et al, 2009):

$$\text{eGFR} = 141 \times \min(\text{Scr}/\kappa, 1)^\alpha \times \max(\text{Scr}/\kappa, 1)^{-1.209} \times 0.993^{\text{Age}} \times [1.018 \text{ if female, } \times 1.159 \text{ if black}]$$

where Scr is serum creatinine, κ is 0.7 for females and 0.9 for males, α is -0.329 for females and -0.411 for males, min indicates the minimum of Scr/ κ or 1, and max indicates the maximum of Scr/ κ or 1.

eGFR using the CKD-EPI equation will be summarized at baseline and may be analyzed as a sensitivity analysis.

Strip Sign for Selected Laboratory Data

For selected laboratory test values that have been received with a qualifier as a part of the result ($>$, \geq , $<$, or \leq), a process to strip the qualifier will be applied and the resulting numeric values will be used for data analysis. The raw value with operator will remain as such in the database and will be used when listed.

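### Hypoglycemia is summarized only with post-rescue events included, and its rate can count events on days that the exposure denominator leaves out

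*SAP*

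**What the plan says.** SAP 4.1.4 excludes efficacy data after the first rescue but keeps safety data: "all safety data (except eGFR) collected during the rescue medication use will be summarized together with data collected prior to the rescue therapy". The reason given is that patients may stay on study drug while rescued. The one exception is eGFR: "The exploratory analysis of eGFR will be repeated twice (once including data after rescue therapy and once excluding data after rescue therapy"). SAP 4.2.5.4 confirms it: "This analysis will be done both excluding data after initiation of rescue therapy and separately including data after initiation of rescue therapy".

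SAP 3.6.4 defines the event: "Rescue therapy is defined as any new antidiabetic concomitant medication or changes to background oral-diabetic medication, for exacerbation of diabetes". It also provides that "Treatment with insulin may be given for emergency reasons during the treatment period", and for background oral agents that "Increases identified as potential rescue episodes will be queried at the site-level to determine whether rescue therapy or not".

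SAP 3.4 lists hypoglycemic events among the safety endpoints, assessed over the treatment period. SAP 4.2.5.2 breaks them down by major or minor, time of day, confirmed or unconfirmed, visit and baseline sulfonylurea (SU) use, but not by rescue. It also gives a "Minor and Major hypoglycemia rate (adjusted for duration of exposure to study drug therapy"), with exposure counted from first to last dose inclusive. SAP 3.6.6 runs the treatment period from first dose "to date of the Week 28 visit, or the ED visit for patients who discontinue the study prior to Week 28", and the last window in Table 10 (hypoglycemic episodes) ends on the last day of that period.

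**The concern.** Insulin and increased oral agents can themselves lower glucose enough to produce hypoglycemia. The SAP treats rescue as a complication for efficacy and for exploratory eGFR. It gives hypoglycemia, the safety outcome most directly exposed to added glucose-lowering drugs, one version only.

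Protocol 5.2 makes the incidence and rate of hypoglycemia a secondary objective to be compared with placebo, and Protocol 4.1 names hypoglycemia with an SU among the main risks. Protocol 11.2.8.4 left the method of comparison to the SAP, which provides descriptive tables, so those tables carry the whole comparison. If exenatide works, rescue may well be more frequent on placebo. Post-rescue events would then raise the comparator's figures and make an exenatide excess look smaller.

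The rate has a second weakness that does not depend on rescue: its numerator and denominator need not cover the same days.

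**Working it through.** **1. No planned figure to reproduce.** Neither document gives a hypoglycemia rate, a rescue rate or a sample size for this endpoint.

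**2. Weight of one patient.** SAP 1.3 gives 122 randomized, 2:1. Placebo: 122/3 = 40.7, about 41; exenatide: 122 − 41 = 81. One placebo patient whose only episode follows rescue adds 1/41 = 2.4 percentage points to placebo incidence.

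**3. Illustration; every input is an assumption.** Let b be incidence without rescue, r the share rescued, and h the chance of a first episode after rescue. Then

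shown incidence = b + (1 − b) × r × h

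shown excess = (bE − bP) − h × [rP(1 − bP) − rE(1 − bE)]

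Take bE = 8% and bP = 5%, a true excess of 3.0 points. For rescue of 5% on exenatide and 15% on placebo, the bracket is 0.15 × 0.95 − 0.05 × 0.92 = 0.0965, so the shown excess is 3.0 − 9.65h points. The brackets for the other rows, found the same way, are 0.0674, 0.1455 and 0.003.

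| Rescue, exenatide vs placebo | h = 1% | h = 5% | h = 20% | h = 40% | Excess reaches zero at |
|---|---|---|---|---|---|
| 3% vs 10% | 2.9 | 2.7 | 1.7 | 0.3 | h = 45% |
| 5% vs 15% | 2.9 | 2.5 | 1.1 | −0.9 | h = 31% |
| 10% vs 25% | 2.9 | 2.3 | 0.1 | −2.8 | h = 21% |
| 10% vs 10% | 3.0 | 3.0 | 2.9 | 2.9 | never |

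Check of one cell (5% vs 15%, h = 20%): exenatide 0.08 + 0.92 × 0.05 × 0.20 = 8.92%; placebo 0.05 + 0.95 × 0.15 × 0.20 = 7.85%; difference 1.07.

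**4. Which h is plausible.** Post-rescue time is limited. Protocol 7.4 discontinues patients for loss of glycemic control, and for metformin or SU added or altered beyond 10 consecutive days or 10 days in 30. Protocol 8.7 calls for consultation once emergency insulin exceeds 10 days in 3 months, so longer use is possible but not automatic. Suppose post-rescue time is 10 days. Against 5% over 196 days (daily hazard −ln 0.95/196 = 0.00026), h = 20% needs −ln 0.80/10 = 0.0223 per day, about 85 times baseline, and h = 40% needs about 195 times. Over 30 days the ratios are about 28 and 65. The right-hand side of the table therefore needs very large hazards, and the left-hand side shows little distortion.

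**5. Rate numerator and denominator.** Set side by side:
- Events: over the treatment period (SAP 3.4), to the Week 28 or early discontinuation (ED) visit (SAP 3.6.6, Table 10).
- Time: last dose minus first dose plus 1 (SAP 4.2.5.2).

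Nothing restricts rate events to dosing days. With D dosing days, g days from last dose to the ED visit and a constant event rate, the calculated rate is too high by the factor (D + g)/D. For example, D = 84 and g = 11 (assumed) give 95/84 = 1.13. Completers are barely affected, because g is about a day. The only discontinuation figure in the documents is about 23% in the exenatide arms (Protocol 11.1, from an earlier study), or 0.23 × 81 = about 19 patients. No placebo figure is given, so the net direction is unknown.

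**The case against.** The strongest reply is that including every event is a legitimate treatment-policy summary of safety, has a stated reason, and matches the treatment-emergent adverse event rule in SAP 4.2.5.1. That stands: the gap is the missing companion table, and the inclusion itself is sound.

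It can also be said that the eGFR parallel is loose. eGFR has an inferential analysis and its own estimands, whereas hypoglycemia is descriptive and sits in SAP 1.1.2 under assessing safety and tolerability. This weakens the charge of inconsistency. It does not remove the practical gap, since Protocol 5.2 asks for the comparison and the descriptive tables are all there is.

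Post-rescue time is limited by the rules in step 4, few patients are involved (15% of 41 placebo patients is about 6), and hypoglycemic events and rescue medications are both listed. All true, and it lowers the likely size. But episodes within the permitted days still count, and listings allow tracing of individuals without giving a between-arm comparison.

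On the rate, Table 10 assigns episodes to visits and does not itself define a numerator. That is fair: the supportable statement is that events after the last dose can be counted, because SAP 3.4 and 3.6.6 set the event period and no text narrows it. A reader might go further and infer that a patient discontinued for missing more than 10 consecutive days must contribute at least 11 uncounted days. The documents do not support this. Such a patient may resume dosing before discontinuation, and SAP 4.2.3 ignores interruptions, so the gap would lie inside exposure.

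**Conclusion.** The point holds as a reporting gap of modest and unknown size. SAP 4.1.4 and 4.2.5.2 give hypoglycemia only with post-rescue events included. If rescue is more frequent on placebo, this can understate an exenatide excess; if rescue is balanced, the difference barely moves; if rescue is more frequent on exenatide, the bias runs the other way. The assumed inputs give distortions from about 0.1 point upward.

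Two stronger readings are tempting. One is that rescue-caused events are charged to the randomized arm; the plan attributes no event to rescue, so only events after rescue can be said. The other is that the pooled table would hide or reverse a true excess. In the middle scenario reversal needs a post-rescue risk above about 31%, which the documents do not support and which the limits on post-rescue time make hard to reach. What rests on the documents' own figures is that one placebo patient is worth about 2.4 points, so even a few such events would be visible.

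The mismatch between rate numerator and denominator holds regardless of rescue, as a possibility that the text leaves open.

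**What to change.** In SAP 4.1.4 and 4.2.5.2:

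- Keep the all-events incidence tables as planned.
- Add a companion set of incidence, episode-count and rate tables, overall and by baseline SU use. Count events from first dose to the earlier of first rescue (the SAP 3.6.4 date) or last dose, and end exposure time at the same point. State how an episode on the rescue date is handled.
- In every rate, count events only over the days in that rate's denominator.

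This needs SAP wording and one more table set from data already collected; no trial procedure changes. The companion tables will hold fewer events. Stopping at rescue is also informative, because rescue follows worsening control, so they should be labelled supportive and should not replace the all-events summary.
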